	gene) of SARS-CoV-2 and for the RNase P gene (RP-gene) from humans to as process
	control and confirmation of the presence of human DNA in the sample.
	Excess material from negative patients will be discharged after testing. Excess
	material from previous positive patients will be discharged. Sample material from

	prospective positive individuals will be treated according to normal practice at the
	local DCM.
	For the retrospective study arm, stored excess material from 200 previously positive
	and 100 negative SARS-CoV-2 samples stored at -80 °C is defrosted on ice and
	checked by RT-PCR to ensure the Cq value. Selected samples are defrosted again on
	ice and aliquoted into 250 μL volume and stored at -80 °C until use. For each test
	one aliquot of each sample is defrosted and 200 µL sample in UTM is tested
	according to the manufacturer's instruction by laboratory trained personnel in
	collaboration between DCM Hvidovre, RH and SSI. One aliquot is used for each test
	and excess material is discharged. One aliquot is retested by RT-PCR after thawing to
	verify the Cq of the sample.
Outcomes	Primary outcome: Performance of each antigen in relation to the RT-PCR test result.
	Secondary outcomes: Performance of each antigen test in relation to the cycle of
	quantification Cq by RT-PCR with and without normalization towards human DNA.
	The fraction of consecutive samples negative for human DNA by RT-PCR.
	Agreement between oropharyngeal swabs and tests from other anatomical test
	locations by RT-PCR.
	Analytical sensitivity and specificity of each antigen test on retrospectively collected
	SARS-CoV-2 positive and negative samples. SARS-CoV-2 positive samples are
	stratified into subgroups according to Cq by RT-PCR.
Participant	Either included when referred to SARS-CoV-2 testing and agrees to participate in the
timeline	testing or being invited as in-patient, by phone or electronically and agrees to
	retesting after a positive SARS-CoV-2 RT-PCR test. Invited in- or out-patients positive
	for SARS-CoV-2 are retested with their consent again as soon as possible after first
	positive RT-PCR test by an outpatient screening team, who visits and samples each
	patient at home or for in-patients by trained hospital personnel.
Sample size	Prospective study arm. 200 SARS-CoV-2 RT-PCR positive and 200 SARS-CoV-2 RT-PCR
Sample size	negative patients included for each antigen test.
	Retrospective study arm. 200 SARS-CoV-2 RT-PCR positive and 100 SARS-CoV-2 RT-

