Da amaitma anat	PCR negative samples retested for each antigen test.
Recruitment	Individuals with suspected SARS-CoV-2 infection referred to a test center are asked
	for participation in the study and given the information for participants. Those
	agreeing for participation in the study sign a consent form. Individuals who test
	positive for SARS-CoV-2 are invited to participate in the study by either 1) personal
	contact with hospital personnel for in-patients, 2) by phone or 3) by electronic
	invitation, which is sent together with the information for participants as a mail in e-
	boks. The mail is sent to the individual by the laboratory or test-center overseeing
	the local testing as an invitation for participation. Individuals are asked to contact the
	local laboratory either by phone or mail, depending on the local setup and to provide
	a phone number to provide further information and planning of additional testing if
	relevant. When retested at the hospital or by the out-patient testing team a signed
	consent form for participation will be collected.

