### Methods: Data collection, management, and analysis

Data collection	RT-PCR result is reported with cycle of quantification Cq for positive tests together
methods	with the Cq for human DNA in the sample.
	Antigen tests are reported according to the manufactor's instruction and divided
	into positive, negative, inconclusive or invalid tests. Inconclusive and invalid tests

	are handled according to the manufactor's instruction. Each antigen test is
	photographed to document the result.
	In the retrospective study arm all antigen tests are tested with stored excess
	material with seeking 50 samples with Cq 20 to 25, 50 samples with Cq 25 to 30, 50
	samples with Cq 30-35 and 50 samples with Cq >35. The 100 negative samples are
	pooled negative samples that are retested by RT-PCR again prior to use.
Data	Written consent for participation and collection of data in the study will be collected
management	at the test center and each consent is marked with the local sample identifier
	number. For consecutive samples each antigen test and the sample for RT-PCR at
	the DTU test center will be marked with the local sample identifier number and data
	will be paired according to this sample identification number. Individuals positive for
	SARS-CoV-2 will be invited in person, by phone or electronically for additional
	testing and individuals who agrees to additional testing, except in-patients will be
	contacted using their self-reported contact information's. The number of individuals
	contacted and rejecting participation will be registered, without additional
	information. At each retest a new sample identifier number will be pair with the
	swab(s) for RT-PCR testing at the DTU test center and the antigen tests conducted
	bedside by trained hospital personnel or outpatient team. Data including photo
	documentation of antigen test results will be send to the steering group and stored
	in a secure regional file archive.
Statistical	Prospective arm: Performance of each antigen test will be reported as sensitivity,
methods	specificity, positive predictive value (PPV) and negative predictive value (NPV)
	compared to oropharyngeal swabs evaluated by RT-PCR. Clinical performance of
	antigen tests will be further evaluated in respect to strong (Cq <25), intermediate
	(Cq 25-35) and weak (Cq >35) RT-PCR tests and in respect to samples with low SARS-
	CoV-2 RNA to human DNA ratio, equal SARS-CoV-2 RNA to human DNA ratio and
	high SARS-CoV-2 RNA to human DNA ratio.

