	Among consecutive collected prospective samples the fraction of samples negative
	for human DNA by RT-PCR will be reported.
	Retrospective study arm: Determination of analytical sensitivity, specificity stratified
	into four groups by PCR (Cq 20-25, Cq 25-30, Cq 30-35 and Cq >35).
	Comparison of sensitivity and specificity between antigen test will be done using
	McNemar chi-squared test. Comparison of PPV and NPPV between antigen test will
	be done by bootstrap test.
	95 % Confidence intervals for sensitivity, specificity, positive predictive value and
	negative predictive value are calculated as bootstrap confidence intervals.

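### Bootstrap 95% intervals are fixed for all four accuracy measures with no exception at 0% or 100%, where they have zero width or do not exist

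*Protocol*

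**What the plan says.** The primary outcome (Outcomes) is "Primary outcome: Performance of each antigen in relation to the RT-PCR test result". Under Statistical methods, performance in the prospective arm is reported as sensitivity, specificity, PPV and NPV. In the retrospective arm, analytical sensitivity and specificity are reported, divided "into four groups by PCR (Cq 20-25, Cq 25-30, Cq 30-35 and Cq >35").

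The protocol has one rule for intervals, at the end of Statistical methods: "95 % Confidence intervals for sensitivity, specificity, positive predictive value and" "negative predictive value are calculated as bootstrap confidence intervals". It names no bootstrap type and no alternative for a proportion of 0% or 100%. It does not say whether intervals are also given within Cq strata.

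The denominators come from Sample size: "Prospective study arm. 200 SARS-CoV-2 RT-PCR positive and 200 SARS-CoV-2 RT-PCR" negative individuals per antigen test, and "Retrospective study arm. 200 SARS-CoV-2 RT-PCR positive and 100 SARS-CoV-2 RT"-"PCR negative samples retested for each antigen test". Data collection methods sets a target of 50 positive samples in each of the four retrospective Cq groups.

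**The concern.** A bootstrap interval takes its width from the variation between resamples. When every result in the denominator is the same there is no variation, and the interval shrinks to a point however many resamples are drawn. Specificity is the measure most exposed, because a test with few or no false positives among 100 or 200 negatives is a realistic result. Where PPV is TP/(TP+FP), zero false positives also fixes PPV at TP/TP in every resample that contains a positive test.

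The estimates and intervals for each antigen test are what this study delivers. An interval of 100–100% from 100 samples tells the reader that false positives are excluded, when the exact interval still allows a false-positive rate of up to 3.6%.

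**Working it through.** **Inputs from the protocol.** Confidence level 95% (two-sided assumed). Denominators: 200 positives and 200 negatives (prospective), 100 negatives (retrospective), target of 50 per retrospective Cq group. The protocol states no interval, precision target or expected accuracy, so it has no figure to reproduce. The true accuracies used below are assumptions, shown as a range.

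**Step 1: the boundary.** With unlimited resamples, the percentile limits for x successes in n are the 2.5% and 97.5% quantiles of Binomial(n, x/n), divided by n. For x = 0 or x = n that distribution is a single point. The Clopper-Pearson lower limit for x = n is 0.025^(1/n), for example 0.025^(1/200) = 0.982.

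| Observed | Percentile and basic | BCa | Clopper-Pearson |
|---|---|---|---|
| 200/200 | 100–100% | undefined | 98.2–100% |
| 100/100 | 100–100% | undefined | 96.4–100% |
| 50/50 | 100–100% | undefined | 92.9–100% |
| 0/50 | 0–0% | undefined | 0–7.1% |

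Crude PPV with no false positives, taking an assumed sensitivity of 50% or 70% of 200, is 100/100 or 140/140. The bootstrap gives 100–100% for both, against Clopper-Pearson 96.4–100% and 97.4–100%. With only 2 true positives and no false positives, about 13% of resamples contain no positive test and PPV is 0/0. NPV with no false negatives likewise gives 100–100%.

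**Step 2: next to the boundary.** Lower limits, percentile against Clopper-Pearson:

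- 199/200: 98.5% against 97.2%
- 198/200: 97.5% against 96.4%
- 99/100: 97.0% against 94.6%

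At 199/200 the basic interval is 99.0–100.5%, which exceeds 100%. The BCa lower limit there is 97.0%, so BCa is sound just off the boundary.

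**Step 3: how often, and the coverage.** The chance of a zero-width specificity interval is p^n (0.99^200 = 0.134; 0.995^200 = 0.367; 0.995^100 = 0.606). Coverage is the sum of Binomial(n, p) probabilities over the counts x whose interval contains p.

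| Assumed true specificity | Zero-width, n=200 | Coverage, n=200 | Zero-width, n=100 | Coverage, n=100 |
|---|---|---|---|---|
| 95% | 0.0% | 96.8% | 0.6% | 95.9% |
| 97% | 0.2% | 93.3% | 4.8% | 94.9% |
| 98% | 1.8% | 90.8% | 13.3% | 86.6% |
| 99% | 13.4% | 86.5% | 36.6% | 63.3% |
| 99.5% | 36.7% | 63.2% | 60.6% | 39.3% |

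Coverage is not monotone, because counts are discrete: at n=200 and 98.5% it is 94.8%. At n=200 and 98%, most of the shortfall is the result 199/200. Its interval starts at 98.5% and misses 98%, and its probability is 200 × 0.02 × 0.98^199 = 7.2%.

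**Step 4: strata, if intervals are given there.** With n=50 and an assumed true sensitivity of 1 / 2 / 3 / 5 / 10% (or 99 / 98 / 97 / 95 / 90%), coverage is 39.3 / 63.5 / 77.8 / 91.1 / 95.7%.

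**Step 5: where there is no problem.** At n=200 and true values of 50 to 90%, percentile coverage is 95.5 to 96.0%.

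**The case against.** The strongest counter-argument is that the low coverage figures at high specificity mostly restate the zero-width chance. At n=200 and 99%, 86.5 + 13.4 = 99.9%; at 99.5%, 63.2 + 36.7 = 99.9%; at n=100 and 99%, 63.3 + 36.6 = 99.9%. Once the count is off the boundary, coverage in those cases is about 99.9%. On that reading the defect is confined to counts of 0 or n, and one line for those counts would do. This is largely right, and the two columns should be read together. It does not dispose of the near-boundary part: at n=200 and 98%, coverage is still 92.4% when the zero-width event is set aside (0.908/(1 − 0.018)).

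It can also be said that the bootstrap type is a detail for the statistical analysis plan, and that a test-inversion bootstrap would return 0.025^(1/200) = 98.2% at 200/200. But that is not what the phrase usually means, and none of the three usual types repairs the boundary. The protocol has already fixed the method for all four measures, so an exact interval at the boundary would depart from its text.

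Three limits stand. How often the event occurs depends on accuracies that the protocol does not give. The stratum figures apply only if intervals are reported by stratum. No decision rule uses a confidence bound. Wilson is not perfect either: its coverage over the specificities listed falls to 91.0%.

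**Conclusion.** The concern holds. Followed as written, the rule gives a wrong interval, or none, whenever a count is 0 or n: 100–100% where the exact interval is 98.2–100% (n=200) or 96.4–100% (n=100). The boundary failure is certain for the percentile, basic and BCa types and rests on no assumption. How often it would occur does: for specificity between 95% and 99.5%, from about 0% to 36.7% per test with 200 negatives, and from 0.6% to 60.6% with 100. Close to the boundary, percentile and basic lower limits sit about 1 to 2.5 percentage points too high in the cases computed (97.5 v 96.4 at 198/200; 97.0 v 94.6 at 99/100). The harm is to reported precision only. Point estimates, mid-range intervals and the McNemar comparisons are not affected. It should be corrected, because these intervals are the study's main statement of uncertainty.

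**What to change.** Replace the interval sentence in Statistical methods with, for example: *95% confidence intervals for sensitivity and specificity (overall and in any stratum where an interval is given), and for PPV and NPV as crude proportions, are Wilson score or Clopper-Pearson intervals.* The final text should name one of the two. Over the specificities listed, Clopper-Pearson is conservative (coverage 96.2 to 98.9%) and Wilson ranges from 91.0 to 96.9%. The bootstrap can stay for comparing PPV and NPV between tests. If PPV and NPV are to be anything other than crude proportions, their interval method needs its own statement, including what is done when a cell is zero.

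The cost is one sentence and somewhat wider intervals near 0% or 100%. Data collection and sample size do not change.

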### Ethics and dissemination

Research ethics	The regional ethics committee in Region Hovedstaden will be contacted for approval
approval	of the involvement of individuals, by direct contact, phone invitation and
	electronical invitations of SARS-CoV-2 positive patients into the study, bed-side
	testing by trained hospital personnel or the outpatient team and the intended
	information for participants in the study.
	The accuracy of antigen tests needs to be clarified to make clear whether antigen
	test or alternative test strategies towards SARS-CoV-2 may be used for rapid
	diagnostics of COVID-19 in the health care system.
Protocol	Protocol modification will be registered, and protocol updates will be shared with
amendments	the trial registry, antigen test providers and the writing group by the steering group

Consent or assent	Will be collected by staff members from the test centers, hospital personnel and the
	outpatient testing team
Confidentiality	Written consent for individuals participating in the study will be marked with sample
	identifier number and will be stored in a secure electronic data structure until a year
	after publication of results. The hard copy of the consent form will be destroyed
	after electronic storage. Consent from any individual initially agreeing to the study,
	but afterwards not meeting the inclusion criteria or retracting consent will be
	destroyed at the local test center at the latest after inclusion of all study participants
	at the local test center and only information about the number of individuals
	retracting consent will be stored.
Declaration of	None of the members of the steering committee have any financial or other
interests	competing interests in any companies providing antigen test to the study. Members
	of the writing group will be asked to declare any financial or other competing
	interests before entering the writing group.
Access to data	The steering group will have access to all data and can share the data as sequential
	data without local sample identifier numbers with the writing group, statistical
	experts and participating antigen test providers when data have been collected and
	analyzed for all participating tests.
Dissemination	Authorship will follow the ICMJE recommendations for authorship. The writing
policy	group will draft and qualify the manuscript but may include professional English
	editing to ensure a more fluent and readable manuscript.
	The results will be published in a peer-reviewed journal as an open access article to
	ensure full access to the results for any person interested in the study.

### Appendices

Informed consent	Attachment 1. Cost estimate.
materials	Attachment 2. Written consent for participation in the study (in Danish)
	Attachment 3. Information for individuals participating in the study (in Danish)
	Attachment 4. Protocol resume
